Study Product(s), Dose, Route, Regimen	Ruxolitinib and enasidenib will be given orally in 28-day cycles. Ruxolitinib dose will be given per protocol, enasidenib will be given at 100 mg daily on enrollment for patients with accelerated and blast phase myelofibrosis regardless of platelet count. Patients with chronic phase myelofibrosis will receive enasidenib at starting dose of 50mg daily for cycle 1. The dose of enasidenib will be increased to 100mg for cycle 2 if the platelet count stays above 50,000 at the end of cycle 1 (Table 3a) and no other therapy emergent SAE of grade ≥ 2 developed (except grade 2 hyperbilirubinemia that is acceptable for dose escalation)

The Tisch Cancer Institute

A Phase II Open-label Study of Combined Ruxolitinib and Enasidenib

in Patients with Accelerated/Blast-phase Myeloproliferative Neoplasm or Chronicphase Myelofibrosis with an IDH2 Mutation

(Myeloproliferative Neoplasms Research Consortium [MPN-RC] 119)

Duration of administration	Duration of treatment anticipated to be at least 6 months. Responders will continue therapy indefinitely unless progression of disease occurs, toxicity warranting discontinuation of therapy is observed, or at the discretion of the treating physician.
	The primary endpoint of this study is best overall response, defined as partial response or better (CR+PR+Cri), and will be defined as the best response by Cycle 6 of combination therapy. All patients meeting the eligibility criteria who have signed a consent form and have begun treatment will be evaluable for response. Any evaluable patient not meeting the definition for response will be deemed as having a non- response.
Statistical Methodology	The largest overall response rate where the proposed combination treatment regimen would be considered ineffective in this patient population is 5%, and the smallest response rate that would warrant subsequent studies with the proposed regimen is 25%. This is based on retrospective analysis applying the 2013 IWG Response Criteria to patients treated with ruxolitinib. A Simon's two-stage minimax design will be employed to test the null hypothesis that the true overall response rate in this patient population is at most 5%.

MPN-RC

MPN-RC A Phase II Open-label Study of Combined Ruxolitinib and Enasidenib Sinai in Patients with Accelerated/Blast-phase Myeloproliferative Neoplasm or Chronic-

phase Myelofibrosis with an IDH2 Mutation (Myeloproliferative Neoplasms Research Consortium [MPN-RC] 119)

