The choice of appropriate treatment options for MF patients is currently based on the prognosis of the individual patient⁸. Several prognostic scoring systems that utilize various clinical parameters including age, leukocyte count, hemoglobin level, platelet count, monocyte count, peripheral blast count, presence of splenomegaly, constitutional symptoms and degree of bone marrow fibrosis (BMF) are helpful in predicting patient outcome^{4,9-11}. Patients under the age of 65 without significant co-morbidities and intermediate/high risk disease by Lille classification or int-2/high risk by IWG-MRT PSS are considered candidates for reduced intensity conditioning stem cell transplant (RIC-SCT). Allogeneic stem cell transplant is the only modality that offers the potential for cure, although the risk of transplant related mortality (TRM) and the morbidity and mortality associated with graft versus host disease (GVHD) are considerable¹². Patients older than 65 or with competing co-morbidities are considered not to be candidates for RIC-ASCT but rather candidates for therapies such as interferon-alfa, immunomodulatory agents (IMiDs) JAK2-TKIs or histone deacetylase inhibitors (HDACI). MF patients that either fail current experimental therapies or are ineligible due to limiting cytopenias often have no alternative treatment options other than agents including hydroxyurea, melphalan, thalidomide, lenalidomide and danazol that achieve response rates of 20-50%, but have not been shown to alter the natural progression of disease^{13,14}.

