8.2 EXCLUSION CRITERIA

- 1. Use of any other standard anti-neoplastic drug or growth factor (e.g., anagrelide, G-CSF, lenalidomide, thalidomide clofarabine) except hydroxyurea or experimental drugs, with the exception of ruxolitinib or enasidenib, less than 14 days or 5-half-lives, whichever is longer, prior to starting study therapy and/or lack of recovery from all toxicity (except for alopecia) from previous therapy to Grade 1 or better.
 - a. Patients will be permitted to receive hydroxyurea while on study for up to a total of 3 cycles of combined therapy.
- 2. Known prior clinically relevant hypersensitivity reaction to ruxolitinib or enasidenib.
- 3. Prior therapy with enasidenib in combination with ruxolitinib.
- 4. Concurrent use of strong inducers of CYP3A4 (Rifampin, St. John's Wort, Carbamazepine, Phenytoin) and/or the following strong inhibitors of CYP3A4 (protease inhibitor containing HIV anti-retrovirals, cobicistat, clarithromycin, itraconazole, ketoconazole, nefazodone, and telithromycin) are prohibited. Also prohibited are CYP2C9 substrate medications that have a narrow therapeutic range: phenytoin and warfarin.
- 5. Any serious medical condition, laboratory abnormality, or psychiatric illness that would prevent the subject from signing the informed consent form, which places the subject at unacceptable risk if he/she were to participate in the study or which confounds the ability to interpret data from the study.
- 6. Lactating females.
- 7. Active uncontrolled infections.
- 8. Patients with active malignancy of other type than required for this study are not eligible with the exception of currently treated basal cell, squamous cell carcinoma of the skin, or carcinoma "in situ" of the cervix or breast. Patients with malignancies with indolent behavior such as prostate cancer treated with radiation or surgery can be enrolled in the study as long as they have a reasonable expectation to have been cured with the treatment modality received.
- 9. Subject has significant active cardiac disease within 6 months prior to the start of study treatment, including New York Heart Association (NYHA) Class III or IV congestive heart failure (Appendix G) acute coronary syndrome (ACS); and/or stroke; or left ventricular ejection fraction (LVEF) < 40% by echocardiogram (ECHO) or multi-gated acquisition (MUGA) scan obtained within 28 days prior to the start of study treatment.

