10.4 CONCOMITANT MEDICATIONS/TREATMENTS

All supportive measures consistent with optimal subject care will be given throughout the study. Concomitant medications will be captured in the Case Report Form (CRF) beginning at Screening. Packed red blood cell or platelet transfusions are allowed when necessary. Growth factor use (including erythropoietin) is not allowed with the exception of the use of filgrastim (G-CSF) or pegfilgrastim, which is permitted ONLY when used to treat febrile neutropenia or in patients who have prolonged (one week or more) Grade 3-4 neutropenia, after approval from the Study Chair.

Concurrent use of strong inducers of CYP3A4 (Rifampin, St. John's Wort, carbamazepine, phenytoin) and/or the following strong inhibitors of CYP3A4 (protease inhibitor containing HIV antiretrovirals, cobicistat, clarithromycin, itraconazole, ketoconazole, nefadozone, and telithromycin) are prohibited. Also prohibited are CYP2C9 substrate medications that have a narrow therapeutic range: phenytoin and warfarin.

The following medications that are known to prolong QT interval are prohibited: amiodarone, arsenic trioxide, astemizole, azithromycin, bepridil, chloroquine, chlorpromazine, cisapride, citalopram, clarithromycin, disopyramide, dofetilide, domperidone, droperidol, erythromycin, escitalopram, flecainide, halofantrine, haloperidol, ibutilide, levomethadyl, mesoridazine, methadone, moxifloxacin, pentamidine, pimozide, probucol, procainamide, quinidine, sevoflurane, sotalol, sparfloxacin, terfenadine, thioridazine, or vandetanib.

Concomitant use of other cytotoxic chemotherapeutic agents (e.g. anagrelide) or other experimental drug or therapy while the subject is on study is prohibited, except for hydroxyurea.

Patients will be permitted to receive hydroxyurea while on study for a total of 3 cycles of combined therapy to control leukocytosis and thrombocytosis at the discretion of the treating physician. Patients who enter study on hydroxyurea will be permitted to remain on hydroxyurea for a total of 3 cycles of combined therapy. Patients who continue to require hydroxyurea after 3 cycles will be removed from study.

Steroids are allowed for the treatment of IDH-Inhibitor Differentiation Syndrome (IDH-DS), if warranted, as standard of care. The use of chronic low-dose steroids to treat an underlying medical condition that is not a malignancy is permitted during the course of study treatment

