10.6 NON-INFECTIOUS LEUKOCYTOSIS

Initiation of treatment with the differentiating agents may lead to rapid WBC expansion not associated with infectious process and not manifesting with the signs and symptoms of IDH-Inhibitor Differentiation Syndrome (IDH-DS) discussed above.

In subjects with elevated WBC, prompt initiation of hydroxyurea is suggested, as per standard local practices (e.g., dose of 2 to 3 g PO twice or three times daily for WBC > 30×109 /L). In case of severe leukocytosis (WBC >100 x 109/L), use of leukapheresis may be appropriate. Subject should be regularly monitored for changes in WBC count and for new signs and symptoms of infection or IDH-Inhibitor Differentiation Syndrome (IDH-DS).

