34.1 APPENDIX A: RESPONSE CRITERIA

Complete Response	As per 2013 IWG-MRT and ELN Criteria
Partial Response	As per 2013 IWG-MRT and ELN Criteria
Clinical Improvement (CI)	As per 2013 IWG-MRT and ELN Criteria
Anemia Response	As per 2013 IWG-MRT and ELN Criteria
Spleen Response	As per 2013 IWG-MRT and ELN Criteria
Symptom Response	As per 2013 IWG-MRT and ELN Criteria
Progressive Disease	 After at least 3 cycles of combined therapy: New splenomegaly that is palpable at least 5cm below the LCM a ≥100% increase in palpable distance, below LCM, for baseline splenomegaly of 5-10cm or a 50% increase in palpable distance, below LCM, for baseline splenomegaly of > 10cm Progression from chronic-phase disease (< 10% blasts) to blast-phase (≥ 20% blasts) disease on two separate CBCs within 28 days For patients in accelerated of blast phase disease at baseline, a doubling of the absolute blast count
Stable Disease	As per 2013 IWG-MRT and ELN Criteria
Cytogenetic Remission	As per 2013 IWG-MRT and ELN Criteria
Molecular Remission	 Complete Molecular remission: eradication of IDH2 and JAK2/MPL/CALR mutations as assessed by both next-generation sequencing and digital PCR assays. Partial Molecular remission: 50% reduction in mutant IDH2 and JAK2/MPL/CALR allele burden as assessed by next-generation sequencing
Cytogenetic/Molecular Relapse	As per 2013 IWG-MRT and ELN Criteria
Complete Blast Response	Absence of circulating peripheral blood blast count with residual features of chronic-phase MPN maintained for at least 28 consecutive days.
Partial Blast Response	Reduction to <4% blast count in peripheral blood with residual features of chronic-phase MPN maintained for at least 28 consecutive days.

A Phase II Open-label Study of Combined Ruxolitinib and Enasidenib Sinai in Patients with Accelerated/Blast-phase Myeloproliferative Neoplasm or Chronic-

phase Myelofibrosis with an IDH2 Mutation

(Myeloproliferative Neoplasms Research Consortium [MPN-RC] 119)

34.2 **APPENDIX B: IWG-MRT AND ELN RESPONSE CRITERIA**

Response categories	Required criteria (for all response categories, benefit must last for ≥12 wk to qualify as a response)
CR	Bone marrow:*Age-adjusted normocellularity; <5% blasts; ≤grade 1 MF† and
	Peripheral blood: Hemoglobin \geq 100 g/L and <unl; <math="" count="" neutrophil="">\geq 1 \times 10⁹/L and <unl;< td=""></unl;<></unl;>
	Platelet count \geq 100 \times 10 ⁹ /L and $<$ UNL; <2% immature myeloid cells‡ and

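### Blast responses (CBR/PBR) reached on permitted hydroxyurea are credited to the combination, because no endpoint or analysis rule says how to classify them

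*Combined protocol and SAP*

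**What the plan says.** Section 6.1, on myelofibrosis patients with no other treatment option, refers to "agents including hydroxyurea, melphalan, thalidomide, lenalidomide and danazol that achieve response rates of 20-50" per cent. Hydroxyurea is the named exception to the washout of other antineoplastic drugs (section 8.2) and to the on-study ban on other cytotoxic agents (section 10.4).

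- Section 8.2: "Patients will be permitted to receive hydroxyurea while on study for up to a total of 3 cycles of combined therapy".
- Section 10.4, use on study: "Patients will be permitted to receive hydroxyurea while on study for a total of 3 cycles of combined therapy to control leukocytosis and thrombocytosis".
- Section 10.4, carried in from before entry: "Patients who enter study on hydroxyurea will be permitted to remain on hydroxyurea for a total of 3 cycles of combined therapy". Anyone who still needs it after 3 cycles is removed from study. The text does not say that the 3 cycles must be cycles 1 to 3.
- Sections 10.5, 10.6 and Appendix D suggest it for differentiation syndrome or a raised white count (section 10.6: "dose of 2 to 3 g PO twice or three times daily"). They do not repeat the 3-cycle limit.

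For the accelerated/blast-phase cohort, the primary endpoint "will be defined as the best response by Cycle 6 of combination therapy" (section 4). Section 22.2 calculates CBR/PBR in the same way as the primary endpoint. Appendix A defines CBR as "Absence of circulating peripheral blood blast count with residual features of chronic-phase MPN maintained for at least 28 consecutive days". PBR has the same 28-day requirement, with blood blasts below 4%. Appendix B requires at least 12 weeks of benefit for its response categories, including CR, PR and CI. Sections 13 and 20 to 22 and the response criteria in Appendices A and B do not mention hydroxyurea.

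**The concern.** In a single-arm trial, every response is attributed to the regimen unless the plan says otherwise. A third drug, allowed expressly to bring counts down, overlaps the period in which response is judged. CR and PR require neutrophils and platelets below the upper normal limit, and CBR/PBR is read from blood blasts alone. The background also counts hydroxyurea among agents that produce responses in myelofibrosis.

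Its use is foreseeable. Section 18.3 lists noninfectious leukocytosis at 8.2% and differentiation syndrome at 14% with enasidenib, and hydroxyurea is the suggested response to both.

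At stake is what the blast-response rate means. It is the secondary efficacy measure for the primary cohort. If some of those responses were reached and held entirely on hydroxyurea, the reported proportion does not describe ruxolitinib plus enasidenib, and a reader of the results could not tell. A rule made after the data are seen would carry little weight.

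**Working it through.** **The plan's own figure.** Section 20.1 enters 13 patients, stops on 0 responses, otherwise goes to 20, and calls the regimen promising at 3 or more. With true rate p:

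- P(stop) = (1−p)^13
- P(promising) = Σ over x = 1 to 13 of C(13,x) p^x (1−p)^(13−x) × P[Bin(7,p) ≥ max(0, 3−x)]

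| p | P(promising), re-derived | Table 6 |
|---|---|---|
| 0.05 | 0.0736 | 0.07 |
| 0.10 | 0.3165 | 0.32 |
| 0.15 | 0.5862 | 0.59 |
| 0.20 | 0.7858 | 0.79 |
| 0.25 | 0.9030 | 0.90 |

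Table 6 is reproduced. The design arithmetic is sound; the gap is in what counts as a response.

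**Inputs for the overlap.** Cycle length 28 days (section 10); hydroxyurea allowance 3 cycles (sections 8.2, 10.4); response window 6 cycles (sections 13.1, 20.1); qualifying periods 28 days (Appendix A) and 12 weeks (Appendix B).

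- Allowance: 3 × 28 = 84 days = 12 weeks.
- Window: 6 × 28 = 168 days = 24 weeks. The allowance is 84/168 = half of it.

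**CBR/PBR.** 28 is less than 84. With continuous hydroxyurea for the full allowance, any blast response that begins within 84 − 28 = 56 days of starting can complete its qualifying period without one hydroxyurea-free day. As written, it counts.

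**CR, PR, CI.** The qualifying period is 84 days and the allowance is 84 days. With continuous use, a response that begins t days after hydroxyurea starts overlaps it for at most 84 − t days and must hold for at least t days without it. Full overlap needs t = 0, meaning every criterion met on the first day. At t = 28, the split is 56 days on and 28 days off. Partial overlap is possible; complete overlap is not realistic.

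**CRi.** It is part of the primary endpoint but is defined in neither appendix, so there is no written qualifying period to compare. That is a separate gap.

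**Can a hydroxyurea-free rule be met?**

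- 28 days: a patient who completes six cycles and uses the full allowance, counted in whole cycles, has 6 − 3 = 3 hydroxyurea-free cycles. Each is 28 days. The rule is feasible.
- 12 weeks: hydroxyurea through cycle 3 leaves 168 − 84 = 84 days, exactly enough with no slack. If the last hydroxyurea day falls after day 84, fewer than 84 days remain, so a later 12-week period cannot finish by day 168. This assumes that the 12 weeks must be completed within the six cycles.

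**The case against.** The case against making more of this is strong, and most of it stands.

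- **The 20-50% does not transfer.** It is a group figure for several agents in myelofibrosis patients who had failed, or could not have, experimental therapy. The sentence goes on to say of these agents, "but have not been shown to alter the natural progression of disease". The two sources cited for it are dated 2003 and 2007, before the 2013 criteria used here. It is not a hydroxyurea rate, and not an accelerated/blast-phase rate. This stands.
- **The cap and the 12-week rule protect CR, PR and CI.** Carried-in use ends at about day 84, and patients who still need the drug are removed. CR and PR also require hemoglobin and platelet floors, a non-palpable spleen and liver, and symptom resolution. Patients already on hydroxyurea at entry have an on-hydroxyurea baseline, which lessens the bias for them. Hydroxyurea may help such a response along, but the documents show no route by which it alone produces one. This stands.
- **A 12-week hydroxyurea-free rule could create bias of its own.** Section 6.3 ties leukocytosis and differentiation syndrome to enasidenib's mechanism, and Appendix D says that the syndrome may appear up to 5 months after starting. Denying primary credit to patients treated for the drug's own effect is a real trade-off. This stands, and is why the fix leaves those definitions alone.
- **CBR/PBR is secondary and has no decision threshold.** True. Its rate is still reported with an interval as evidence of efficacy, so its meaning matters.
- **Section 22.2 also refers to the position after 6 cycles.** Read as status at that point, carried-in use would be over. Hydroxyurea used in later cycles would still overlap, and the same paragraph has CBR/PBR calculated like the primary best response.

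**Conclusion.** The point holds for CBR/PBR. A 28-day qualifying period can lie wholly inside up to 84 permitted hydroxyurea days, and the plan credits it. CR, PR and CI are exposed only in part. The chronic-phase CI rate still deserves a check, because 1 response in 9 is read as activity, so a single classification can decide that cohort.

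A reader might infer more from Table 6: if hydroxyurea lifted an ineffective regimen from 5% to 10% or 15%, the chance of a promising result would rise from 7% to 32% or 59%, and the stated 0.10 level would be passed at about 5.7%. The documents do not support that step. They give neither the share of patients who will take hydroxyurea nor the share of those who would gain a CR, PR or CRi from it, and they do not show whether the ruxolitinib series behind the 5% null allowed it. Those figures describe how the design behaves at other true rates. They do not measure hydroxyurea's contribution.

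The size of the effect on the CBR/PBR rate is also unknown. What is established is that the plan cannot separate the two sources. The conclusion assumes 28-day cycles and that hydroxyurea given under sections 10.5, 10.6 and Appendix D counts towards the 3-cycle cap. If it does not, the possible overlap is longer.

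**What to change.** Make two changes, both to the analysis only.

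1. **CBR/PBR (section 22.2).** Credit a CBR or PBR only when its 28 consecutive qualifying days contain no hydroxyurea. Report the as-written rate beside it.
2. **Primary CR/PR/CRi and chronic-phase CR/PR/CI.** Leave the definitions unchanged. Pre-specify a sensitivity analysis that counts as non-response any response whose qualifying period overlaps hydroxyurea. For every responder, list hydroxyurea dates against response dates. CRi needs a written qualifying period before this analysis can be applied to it.

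Section 10.4 already has concomitant medications recorded on the CRF from screening, so the cost is a short addition to section 22 and one extra table. The downside is that a CBR or PBR may be credited later, or lost in a patient who stops early. Intermittent hydroxyurea could also break up an otherwise qualifying run. The as-written rate, reported alongside, shows how often this happens.

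Neither change affects when hydroxyurea may be given or who continues treatment after cycle 6.

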6.2 RUXOLITNIB

MPN-RC

JAKs play an important role in signal transduction following cytokine and growth factor binding to their receptors. In addition, JAKs activate a number of downstream pathways implicated in the proliferation and survival of malignant cells including the STATs (signal transducers and activators of transcription), a family of important latent transcription factors. Aberrant activation of JAKs has been associated with increased malignant cell proliferation and malignant cell survival in patients with Philadelphia chromosome negative MPD. The finding that peripheral blood from myeloproliferative disease (MPD) patients is capable of forming erythroid and megakaryocyte colonies in the absence of exogenous factors (which signal through JAKs) suggests that cells from these patients are intrinsically different than normal cells. Indeed, work from a number of laboratories led to the identification of multiple somatic mutations in genes associated with cytokine and growth factor signaling. These include a mutation in the pseudo-kinase domain of JAK2V617F (amino acid 617, valine to phenylalanine) that results in constitutive activation of JAK2 and downstream STATs. This mutation was found in > 90% of all PV patients and

A Phase II Open-label Study of Combined Ruxolitinib and Enasidenib Sinai in Patients with Accelerated/Blast-phase Myeloproliferative Neoplasm or Chronic-

phase Myelofibrosis with an IDH2 Mutation (Myeloproliferative Neoplasms Research Consortium [MPN-RC] 119)

in approximately 50% of all ET and Myelofibrosis with Myeloid Metaplasia (MMM) patients. More recently, other mutations have been identified in MPD patients lacking the JAK2V617F mutation. For instance, additional activating mutations in JAK2, as well as a mutation in the thrombopoietin receptor (MPL) and calreticulin (CALR) result in constitutive ligand- independent JAK activation. Importantly, ectopic expression of each of these mutant genes has been demonstrated to be sufficient to cause MPN-like syndromes in mice. Moreover, even in MPN patients lacking a confirmed JAK2 mutation, the detection of STAT activation suggests dysregulated JAK activity. In fact, regardless of the mutational status of JAK2, the malignant cells expectedly retain their responsiveness to JAK activating cytokines and/or growth factors; hence, they may benefit from JAK inhibition. These findings, in addition to the limited life span of these patients and lack of beneficial therapies for the treatment of PMF and post-PV/ET MF, clearly support the use of a JAK inhibitor in these diseases.

Ruxolitinib is a JAK1/2 inhibitor that is currently FDA-approved for the treatment of patients with intermediate and high-risk MF (as well as PV patients with inadequate response to or are intolerant of hydroxyurea). Ruxolitinib is a substituted pyrrolopyrimidine compound that acts as a potent and selective inhibitor of the Janus kinase family of enzymes. Ruxolitinib is a novel, potent, and selective inhibitor of the JAKs with modest selectivity for JAK2. Ruxolitinib potently (IC50 values < 5 nM) inhibits JAKs, yet it does not significantly inhibit (<30% inhibition) a broad panel of 26 other kinases when tested at 200 nM (approximately 100 times the average IC50 value for JAK enzyme inhibition). Moreover, in cell-based assays relevant to the pathogenesis of MPDs, such as JAK-STAT signaling and the growth of cytokine-dependent lines, ruxolitinib demonstrated excellent potency (IC50 values of 80-141 nM). This effect was not due to general cytotoxicity, because ruxolitinib (up to 25 μ M) had no significant effect on the growth of cytokine-independent cell lines transformed by the Bcr-Abl oncogene. In addition, ruxolitinib inhibited JAK/STAT signaling and growth of a cell line expressing the JAK2 mutant variant (JAK2V617F) that has been implicated in the pathogenesis of the majority of Philadelphia chromosome negative MPN. Additional details as to the *in* vitro pharmacology of ruxolitinib may be found in the Clinical Investigator's Brochure (IB). Ruxolitinib was evaluated in two mouse models where either a cytokine-dependent multiple myeloma cell line, INA-6, oracell line, BaF3, engineered to express JAK2V617F was inoculated. The ability of ruxolitinib to inhibit JAK pathway signaling as well as tumor cell survival and growth was assessed in vivo. In vitro cell biology experiments have demonstrated that the potency of ruxolitinib is very similar between the cytokinedependent INA-6 myeloma cells, with wild type JAKs, and the BaF3 cells expressing a clinically relevant mutant JAK2. As such, the in vivo studies described herein characterize the ability of ruxolitinib to inhibit wild type JAK2 (using the INA-6 xenograft model) and MPD-related mutant JAK2 (using a mouse model of splenomegaly driven by cells expressing the mutant JAK2V617F).

Treatment of mice with orally administered ruxolitinib resulted in a dose-dependent suppression of STAT3 phosphorylation and tumor growth in the cytokine-dependent INA-6 xenograft model at doses ≥ 10 mg/kg BID. Moreover, oral administration of ruxolitinib inhibited the dramatic splenomegaly in mice resulting from intravenous inoculation of the BaF3-JAK2V617F cells. Additional details as to the *in vivo* pharmacology of ruxolitinib may be found in the Clinical Investigator's Brochure (CIB). In summary, pharmacological data obtained in both *in vitro* and *in vivo* model systems support the potential utility of orally administered ruxolitinib in the treatment of malignancies, including MPD such as PMF and Post-PV/ET MF.

The chemical name of ruxolitinib phosphate is (R)-3-(4-(7*H*-pyrrolo[2,3-*d*] pyrimidin-4-yl)-1*H*-pyrazol-1-yl)-3-cyclopentylpropanenitrile phosphate. Ruxolitinib phosphate has a molecular formula of C17H21N6O4P and a molecular weight of 404.36. Ruxolitinib phosphate drug substance is a white to off-white powder and is referred to herein as ruxolitinib.

